# 10.2 Causality

This study uses the following instruction to assign causality to report SAE (31)

| Relationship   | Description  |
|----------------|--|
| Unrelated      | No evidence of any causal relationship between the AE and the trial                  |
|                | medication/study intervention  |
| Unlikely       | Little evidence to suggest there is a causal relationship (e.g., the event did not   |
|                | occur within a reasonable time after administration of the study product) or there   |
|                | is another reasonable explanation for the event (e.g., the participant's clinical    |
|                | condition or other treatment).   |
| Possible       | There is some evidence to suggest a causal relationship with the study product       |
|                | (e.g., because the event occurs within a reasonable time after administration of the |
|                | study product), but the influence of other factors may have also contributed to the  |
|                | event (e.g., the participant's clinical condition or other treatments).              |
| Probable       | There is evidence to suggest a causal relationship with the study product and that   |
|                | the influence of other factors is unlikely.  |
| Definite       | There is clear evidence to suggest a causal relationship with the study product and  |
|                | that other possible contributing factors can be ruled out.                           |
| Not Assessable | There is insufficient/incomplete evidence to make a clinical judgment of a causal    |
|                | relationship   |

# 10.3 Expectedness

It is expected that participants in the trial will have a range of underlying comorbidities; therefore, adverse events that are deemed expected for this population (see section 10.3.2) will not be reported. However, there may be pre-specified adverse events expected based on the manufacturing information and current evidence studies of the study product that should be recorded and reported. The procedure to report and the record are covered separately elsewhere in this document (see section 10.5).

#### 10.3.1. Summary of current manufacturer's information

SACCO System's safety information sheet published in 2016 states that the probiotic product *Lactobacillus rhamnosus* is not hazardous and is well tolerated even among children aged 1-5 years. Rare cases of secondary infection have been reported in immunosuppressed patients, but since the trial excludes residents with any immune compromised medical condition, we, therefore, do not expect any adverse events based on the current manufacturer's information.

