# TRIAL SUMMARY

[figure not shown]
| Title                | Improving the oral health of older adults using milk supplemented with fluoride and probiotics: An interventional feasibility study and pilot RCT   |
|----------------------|---|
| Acronym              | ELDER   |
| Short title          | ELDER   |
| Trial configuration  | Multi-centre, open-label, parallel-group, four-arm, prospective, cluster-randomised, placebo-controlled feasibility trial   |
| Trial setting        | Care homes in TeesValley (residential, nursing, mixed)  |
| Planned sample size  | 240 participants  |
| Eligibility criteria | 
 
Care Home (cluster level) criteria:         Inclusions         
 
Site: Tees Valley care homes for older people, with, without nursing or mixed
 
Size: ≥ 5 resident beds in the care home in total with mental capacity
 
 
 
Exclusions
 
 |
|                      | 
 
Care homes not located within the Tees Valley region
 
Care homes with inadequate resident capacity where there are < 5 beds in total
 
   |
|                      | Care Home Resident criteria at trial entry:   |
|                      | 
 
Inclusions
 
Full-time resident in a care home
 
Age ≥ 65 years
 
   |

|  | No acute or immunocompromised medical   |
|--|---|
|  | condition   |
|  | Able to give informed consent for participation   |
|  | Tolerance for dairy products  |
|  |   |
|  | Exclusions  |
|  | Residents who are receiving planned respite or end-   |
|  | of-life or palliative care  |
|  | • Residents who are < 65 years of age   |
|  | Residents with any immunocompromised medical conditions   |
|  | Residents who lack the mental capacity to provide   |
|  | informed consent  |
|  | Residents who are currently taking/being prescribed   |
|  | regular probiotics  |
|  | Residents with severe lactose intolerance   |
|  | Residents who do not have a working level of oral   |
|  | English   |
| Follow-up duration                     | The recruitment window will be open for three months from the official trial start date, and the follow-up schedule will begin from the time the participant gives written informed consent and would from then depend on the length of time the participant remains active in the trial.   |
|  | rengar of time the participant femalis active in the than.  |
|  | Participants will have a baseline assessment and endpoint assessment after nine months.   |

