# 2.4 Outcome Measures

The primary endpoints will be:

- i. Acceptability of the supplemented milk and compliance with the intervention programme
- ii. Potential clinical dental results of the intervention, including root caries and gingival inflammation
- iii. Bacterial and fungal counts in saliva and supragingival plaque at baseline and over a subsequent 9-month period

The secondary endpoints will be:

- i. Frequencies of infection
- 1. Use of antibiotics and unscheduled pain killers
- 2. Urgent care appointments (medical/dental) over the 9-month period of intervention

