# 5. Trial Population

Care home residents in Tees Valley region of North East England. The residents (individual level) will be eligible to participate if they meet all of the inclusion criteria and may not enter the trial if any of the exclusion criteria listed apply.

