#### Exclusion criteria

- Residents who are receiving planned respite (temporary care home resident) or end-of-life or palliative care
- Residents who are < 65 years of age
- Residents with any immunocompromised medical condition
- Residents who lack the mental capacity to provide informed consent
- Residents who are currently taking/being prescribed regular probiotics
- Residents with severe lactose intolerance
- Residents who do not have a working level of oral English

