# 8. Trial Intervention

The consented care homes will be assigned randomly to one of the study arms: - (a) Group 1: non-supplemented milk (placebo), (b) Group 2: milk supplemented with fluoride (5.0 mg F/l), (c) Group 3: milk supplemented with probiotics (Lactobacillus), and (d) Group 4: milk supplemented with fluoride and probiotics. All subjects will be asked to drink a glass of plain/supplemented milk once daily, five days a week, for nine months. Fluoridated milk or probiotics, or placebo (referred to as the Study product) will be administered by the resident's routine caregiver during medicinal/meal rounds. The study product will be sourced from the manufacturer and transported to the study site. Fluoridated milk will be distributed in a small carton, and the probiotics will be provided as a powder in sealed sachets. The preferred route of administration is as follows:

1. The carton containing fluoridated milk is to be emptied into a tall glass and then consumed.

2. The probiotic powder is to be dispensed in a spoon, then added to a prepared glass of skimmed milk/fluoridated milk, mixed well and then consumed

Each care home will be provided with the manufacturer's dossier detailing the composition of the probiotic form and fluoridated milk. After allocation, probiotic sachets will be distributed to the care home at the beginning of the trial, whereas milk (both skimmed & fluoridated) will be distributed to the trial sites weekly. Participants admitted to the hospital would not be expected to continue taking the study product during their hospital stay.

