All samples of saliva collected will be cultivated at 37°C for 48h and 96h to measure bacterial and fungal growth. All oral examination, recordings and biological sample collection will be performed by a senior dentist both at baseline and after a subsequent follow-up period of 9 months. A dental hygienist will also be present (not necessarily at all sites) to assist with data collection. The dental examiner, after completing the oral examination, will give these to the trial staff delegated to the respective trial site. The dental assessment will be recorded in a specifically designed record sheet which will be sent to the coordinating centre periodically after completion. All samples/data will be labelled with participant study ID before being sent to the coordinating centre for filling/storage and analysis. Only the research team and laboratory staff at the coordinating centre will have access to trial specimens. The CTC will ensure that the storage, analysis, and disposal of all biological samples will meet the requirements of the Human Tissue Act, 2004. Data collected will be transferred to trial-specific password-protected Excel files with the help of the CTC for subsequent data analysis.

• Medical and dental records: Participants' medical and dental background data will be collected from the care home records and continuously updated during the course of the trial. The dental history collected will include but is not limited to the number of reported episodes of tooth pain, discomfort, sepsis, and unscheduled visits to a dental office. In addition, general medical information such as data on non-scheduled medical episodes, use of pain medication, data on the frequency, recency, and occurrence of bacterial or fungal infections, report of any common bowel problems, domiciliary visits, and hospital admissions will be recorded monthly by the delivery staff into the relevant trial form. The dentist or any member of the research team will collect this information at baseline and then after nine months.

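### Section 9.2 has no action for a Group 3 or 4 resident who becomes immunocompromised, or starts immunosuppressive treatment, while taking the probiotic

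*Protocol*

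**What the plan says.** On the risk, section 10.3.1 reports from the manufacturer's information that "Rare cases of secondary infection have been reported in immunosuppressed patients". It then reasons that the trial "excludes residents with any immune compromised medical condition, we, therefore, do not expect any adverse events based on the current manufacturer's information".

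On eligibility, the exclusion in section 5 reads "Residents with any immunocompromised medical condition". The Trial Summary heads the list "Care Home Resident criteria at trial entry", and section 5 says that residents "may not enter the trial if any of the exclusion criteria listed apply".

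On exposure, section 8 gives the probiotic to Groups 3 and 4, once daily on five days a week for nine months. The Trial Summary ends dosing at 30/12/23 if that comes sooner. Section 8 also says that "the probiotics will be provided as a powder in sealed sachets", to be stirred into the milk.

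On stopping, section 9.2 ends the intervention, apart from the resident's own choice, for three events: a positive CV-19 test; prolonged hospitalisation for a reason not diagnosed at recruitment; and an unexpected series of adverse reactions to the product. Section 8 adds that residents are not expected to take the product while in hospital.

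**The concern.** The exclusion is the reason section 10.3.1 gives for expecting no adverse events from the manufacturer's information. An entry criterion protects residents on the day they enter. Over up to nine months a person aged 65 or over in a care home may receive a new diagnosis or start a treatment that suppresses immunity. From then on the reasoning in 10.3.1 no longer applies to that resident, yet the protocol as written lets the probiotic continue with no required pause or review.

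At stake is the safety of a few residents in two of the four arms. Sections 10.3.1 and 5 also describe the group differently. The risk is stated for immunosuppressed patients, which can include people immunosuppressed by treatment, while the exclusion names a medical condition. Whether a resident already on such treatment may enrol is therefore open.

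**Working it through.** There is no plan figure to reproduce, and no calculation decides the point. The check sets the relevant sections against two questions: is a change in immune status likely to become known, and does anything then have to happen?

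**1. When the exclusion applies.** The Trial Summary and section 5 both tie it to entry. No section calls for eligibility to be checked again during dosing.

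**2. The termination list in 9.2.** Each event is tested against a new immunocompromising diagnosis or a new immunosuppressive treatment:

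| Event in 9.2 | Does it cover the case? |
|---|---|
| Positive CV-19 test | No |
| Prolonged hospitalisation, reason not diagnosed at recruitment | Only if the change comes with a long admission |
| Unexpected series of adverse reactions | Only after harm has occurred |

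None of the three is about immune status.

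**3. The hospital rule in section 8.** Dosing stops during the stay. A resident discharged on immunosuppressive treatment after a short stay may resume the product.

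**4. Routes by which the team could learn of the change.**
- Adverse event reporting (10.1, 10.5.1): a new diagnosis would probably meet the definition. None of the 16 events that section 10.6 exempts from reporting concerns immune status. Care home staff report immediately or at the monthly visit.
- Record updates (9.1): medical background data are updated throughout and "general medical information such as data on non-scheduled medical episodes, use of pain medication" are recorded monthly. The list is given as examples, so other medicines are not ruled out.
- Source documents (section 17): prescriptions and laboratory results are named among them.
- Site visits (13.1): two or three a month, with a check that source documents and trial records are accurate.

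**5. Required action.** These routes record, check or review. None obliges anyone to pause the sachet. Section 10.5.3 recognises product-related infection as a serious adverse reaction, but that applies after the infection. Section 15.5 lets the coordinating centre seek urgent advice from the Data Monitoring Committee, but names no individual trigger.

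**6. Who the rule would concern.** With 240 residents planned and four arms, and assuming full recruitment and equal arms, Groups 3 and 4 hold 240 / 4 × 2 = 120 residents. The protocol gives no rate of new immunocompromise, so the share affected cannot be worked out.

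**The case against.** The best case against the point is that 10.3.1 is not wrong. It sits under Expectedness, speaks only of the manufacturer's information, and is supported by the literature summary in 10.3.2 and the product description in 10.4. Section 9.2 does not forbid a clinician from stopping the product. The harm is called rare. On this view the proposal adds detail and does not correct an error. Much of this stands: there is no outright contradiction between 10.3.1 and 9.2, and the priority should be low. It does not remove the gap. Section 9.2 already names individual health events that end dosing and omits the one risk group that the safety text identifies.

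Three stronger readings are tempting, and the protocol does not support them.

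- A reader might infer that a new immunosuppressive medicine would go unnoticed, because section 2.4 names only "Use of antibiotics and unscheduled pain killers" and section 9.1 names only pain medication. But the 9.1 list is open, section 17 makes prescriptions source documents, and section 13.1 has source documents checked two or three times a month. The product is also given on medicine or meal rounds (section 8), so the caregiver may know of the medicine.
- A reader might infer that one resident's dosing would wait for a half-yearly committee meeting. Section 15.5 provides for urgent contact and emergency meetings between them.
- A reader might want an expected number of affected residents or of further doses taken. Nothing in the protocol supports an incidence, so any such number would be invented.

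**Conclusion.** The point holds as a missing required action. The only preventive control for the risk named in 10.3.1 applies at entry; none of the three events in 9.2 concerns immune status; and no section requires the probiotic to be paused or reviewed for a resident who enters the risk group during dosing. A statistical analysis plan would not normally set individual stopping rules, so the gap is unlikely to be closed there.

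Its size cannot be put in residents or infections. The priority is minor: the harm is described as rare, the team could learn of the change by several routes, and a clinical decision to stop remains possible. The conclusion assumes that no document outside the protocol, such as a site procedure or the unseen Monthly Record, already directs a pause. It does not depend on a change going undetected.

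**What to change.** Make three linked changes.

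1. **Section 9.2:** add that a new immunocompromising diagnosis, or new systemic immunosuppressive treatment, in a Group 3 or 4 resident pauses the probiotic sachet pending prompt review by the Chief Investigator. Whether to stop for good remains a clinical decision. Because the sachet is separate, the milk and all follow-up continue.
2. **Section 5:** word the exclusion to cover systemic immunosuppressive treatment as well as a condition. Otherwise a resident on such treatment at baseline might enrol and continue while one who starts it later is paused.
3. **ELDER Monthly Record:** if not already there, add one prompt asking about a new immunocompromising diagnosis or medicine since the last visit.

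The cost is one sentence in 9.2, a few words in section 5 and at most one form item, completed by staff who already visit each site. There is a slight data burden. Measured compliance in Groups 3 and 4 could fall slightly, because section 8.2 counts days on which the allocated milk is drunk. If dosing has already ended, the same wording should go into the definitive trial's protocol.

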# 10.3.2. Summary of current literature

Following an extensive review of current literature and also based on the evidence published by a recent article (32) that critically appraised all probiotics used for oral health, we conclude that the

probiotics strain used in ELDER is generally safe and well tolerated among both infants and the elderly.

Minor gastrointestinal symptoms such as abdominal cramping, bloating, soft stools, flatulence, and taste disturbance have been reported (33). If these events were to occur, they would be classed as expected AEs and would be classed as unexpected if these events were to meet the definition of SAR.

# 10.4 Reporting Period

The adverse event reporting period for this study begins as soon as the resident provides informed consent and ends one month after the final data collection. The study products (probiotics and fluoridated milk) being used in this trial is a well-established food supplement, and given the frailty of the study population with a wide range of healthcare needs, it's critical not to cloud any true emerging safety signals by collecting unrelated data. Therefore, safety reporting in this study will focus on SAEs that could be related to the study population, and only SARs that could be related to the study product will be assessed for expectedness. The onset of any AE will be apparent particularly to care home staff, as they know their residents and their medical conditions thoroughly and so can quickly identify any deterioration to a resident's health very early. The care home staff will be informed of the pre-specified events that could be expected with the study.

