# 3. Trial Design

It is a multi-centre, open-label, parallel-group, four-arm, prospective, cluster-randomised, placebo-controlled pilot trial aiming to recruit at least 240 Care Home Residents (CHR). A cluster randomised trial is required, as an individually randomised trial would be subject to the threat of contamination (unintentional drop out and drop in across treatment arms due to mixing up milk) and managing four different kinds of milk within a single care home would be infeasible.

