#### 6.4 Randomisation

The unit of randomisation is the care home (cluster). The care homes will be randomised based on a 1:1 ratio to each available intervention arm or control arm. Trial staff at each trial site will inform the coordinating centre when there are four eligible care homes as they will be randomised in a set of four or six if two sister care homes belonging to the same chain are recruited. As the unit of randomisation is a care home, and the number of participants in each care home is expected to vary, blocking will be used to ensure a close balance of the number of participants (and not necessarily care homes) assigned to each arm. The allocation for a particular trial site will only be revealed after gaining informed consent (i.e., both at the care home level and the individual participant level) and baseline data collection. This approach reduces the threat of post-randomisation selection bias in cluster trials, as individual participants consent to be randomised to one of the four arms rather than being told which arm they have been allocated to if consent is only sought at the level of the care home.

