#### 6.5 Blinding and concealment

As the ELDER trial is an open-label study, the participants, care home staff, and trial team (including the trial statistician and RNs conducting all assessments) will not be blinded to intervention assignment

due to the nature of the trial procedure. However, the dentist performing the baseline and follow-up dental examination will be blinded to intervention and outcome assignment. Release of allocation only following enrolment, resident consent, baseline data collection, and dynamic randomisation of care homes using minimisation will ensure allocation concealment.

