#### 11. Statistical considerations

# 11.1 Sample size

The sampling frame adopted for this study is a non-random convenience sampling, depending on the availability within the 3-month recruitment window and their acceptance to participate in the study. This pilot RCT is not powered to detect intervention effects. The size of the study is sufficient to address the primary feasibility outcomes of acceptability of/compliance with the intervention and whether the potential oral health outcomes for a subsequent definitive trial can be captured robustly. The aim is to recruit up to 10 care home residents per home (a minimum of four and a maximum of fifteen) from care homes resulting in an estimated recruited sample of 240. This calculation was based on the calculations of a four-arm trial with three experimental treatments, with a normally distributed outcome, a standardised value of 0.6 being considered an interesting treatment effect, a significance level of 0.05, and Bonferroni's correction for multiple testing. The sampling size estimation was based on the required number of clusters (care homes) with an average consenting participant of 10.

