# 15.5 Data Monitoring Committee

The Data Monitoring Committee (DMC) will be established to oversee the safety and design of the study. The members of the DMC are a small group of three members – two members from the coinvestigator team and a third member who would be completely independent of the trial. The rationale not to have a mixed DMC and rather have all independent members is that the ELDER STUDY is a

feasibility trial, and the primary objective is to refine the overall structure and procedure for a definitive trial.

As highlighted in the above session, the DMC takes up an advisory role to the SSC and offers recommendations on all matters relating to patient safety and reporting. Therefore, the committee will take responsibility for reviewing safety data reporting of AEs and line-listings of reported SARs captured throughout the trial and, if the need arises, request further analysis. Furthermore, apart from monitoring for safety signals, the DMC will also be asked to a) advise on whether the data collected is valid by verifying for completeness and accuracy; b) assesses the accumulated data for scientific merit to justify the continuing recruitment of further participants; and finally, c) monitor if clinical equipoise was maintained throughout the duration of the study.

The DMC will be asked to convene at least twice a year and provide advice to the SSC. In case of safety issues, an emergency meeting will be called for. The Coordinating Centre will be in constant communication by emails and telephone with DMC to seek advice on urgent matters, such as when a participant's safety is threatened.

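### Safety reporting filters events by presumed cause and leaves the randomised plain-milk arm unused, so an excess of common serious events could be missing from the AE/SAE data or the SAR listing

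*Protocol*

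**What the plan says.** All references are to the protocol.

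- **Rationale (10.4).** Residents are frail and have many health events, so reporting is narrowed "not to cloud any true emerging safety signals by collecting unrelated data".
- **Events set aside (10.6).** A list of events common in care homes is deemed unrelated and is not to be reported as an AE or SAE. It includes cardiovascular events, falls with or without fracture, delirium and dehydration. No exception is made for seriousness. Section 10.5.1 applies the same exclusion to AE reporting by care home staff.
- **SAE collection (10.5.2).** All SAEs are to be collected monthly and then graded for causality, down to not related. No exception for the 10.6 list is stated.
- **Becoming a SAR (10.5.3).** An SAE counts as a SAR only if judged probably or definitely related. The accompanying parenthesis points to confirmed septicaemia or identification of the product strain.
- **Who judges.** Delivery staff and the trial coordinator grade the event and the chief investigator confirms it. Section 6.5 says the trial team, including "RNs conducting all assessments) will not be blinded to intervention assignment".
- **DMC (15.5).** It reviews AE reporting and "line-listings of reported SARs captured throughout the trial", and may ask for further analysis.
- **Control arm (8).** The first arm is "a) Group 1: non-supplemented milk (placebo".
- **Other data.** Under 9.1, "hospital admissions will be recorded monthly by the delivery staff into the relevant trial form". Section 2.4 makes infections, antibiotic use and urgent care appointments secondary endpoints.

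**The concern.** The argument in 10.4 would suit a single-arm study, where background illness can be removed only by judging each event. Here a concurrent randomised arm carries the same background. A supplement that raises the rate of a common event produces individual cases that look like ordinary cases. Only a difference in counts between arms reveals it.

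The text as written works against that comparison at three points. Listed events may never enter the AE/SAE data. Other events must be rated probable or definite to reach the SAR listing, and the raters know the arm and treat residents whose comorbidities offer another explanation for most events. The DMC's named material contains no comparison with plain milk. At stake is whether the pilot's safety statement, which will inform a definitive trial, uses its randomised control.

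**Working it through.** **1. Arm size.** Section 3 describes a "four-arm, prospective, cluster-randomised, placebo-controlled pilot trial aiming to recruit at least 240 Care Home Residents (CHR". Section 6.4 says: "The care homes will be randomised based on a 1:1 ratio to each available intervention arm or control arm". So 240/4 = 60 residents per arm. Section 11.1 gives an average of 10 per home, so 60/10 = 6 homes per arm.

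The 240 can be approximated from "a standardised value of 0.6 being considered an interesting treatment effect, a significance level of 0.05, and Bonferroni's correction for multiple testing". With two-sided alpha 0.05/3 and 80% power (an assumption, as no power is stated), n = 2(2.394 + 0.842)²/0.6² = 58.2, rounded up to 59 per arm. Four arms give 236. Other assumptions also give 236. The figure matters here only for arm size.

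**2. What attribution would show.** The protocol gives no event rates and no ICC, so all rates below are assumptions. Take a nine-month risk of a serious event of 20% on plain milk and 40% on one supplemented milk: 12 v 24 residents, an excess of 12.
- If the events are on the 10.6 list, none is reported as an AE or SAE.
- If they are not, suppose each of the 12 extra events is rated probable or definite with chance q. The chance that none of them becomes a SAR is (1 - q)^12, which is 54% at q = 0.05, 28% at q = 0.10 and 7% at q = 0.20.

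**3. What a by-arm count would show, one arm v plain milk.**
- SE ignoring clustering: sqrt((0.2×0.8 + 0.4×0.6)/60) = 0.0816.
- Design effect at ICC 0.05: 1 + 9×0.05 = 1.45, so SE = 0.0816×sqrt(1.45) = 0.0983.
- Six homes per arm leave 2×6 - 2 = 10 df, with t = 2.23. Half-width = 0.0983×2.23 = 0.219.
- Difference +20 points, 95% CI about -2 to 42. The normal quantile 1.96 gives a half-width of 0.193 and about 1 to 39, which is too narrow for so few homes.

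**4. Power, normal approximation.** Power = Φ[(difference - 1.96×SE0)/SE1], where SE0 uses the pooled risk and SE1 the separate risks.

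| Risks | ICC 0 | ICC 0.05 |
|---|---|---|
| 20% v 40% | 67% | 51% |
| 10% v 20% | 33% | 24% |

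These are somewhat optimistic with 6 homes per arm.

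**5. Pooled contrasts (120 v 120, 12 homes each, 22 df, t = 2.07, ICC 0.05).**
- Both arms with the supplement at 40%, the other two at 20%: SE = sqrt(0.40/120)×sqrt(1.45) = 0.0695; half-width 0.144; +20 points, CI about 6 to 34.
- Excess in one arm only: the pooled risks are 30% v 20%. SE = sqrt((0.21 + 0.16)/120)×sqrt(1.45) = 0.0669; half-width 0.139; +10 points, CI about -4 to 24.

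Pooling helps if the excess follows the supplement and dilutes it if it is confined to one arm.

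**6. The two collection rules.** Take a fall with fracture that leads to admission. It meets the SAE definition in section 10.1 through hospitalisation. Section 10.5.2 would have it collected; 10.6 says it is not reported as an SAE. Both cannot be followed.

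**The case against.** A reader might infer that any excess of serious events would go unseen, or that the randomised comparison is thrown away altogether. The documents do not support that.

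- Section 10.5.2 collects all SAEs before grading them, and takes the higher causality category when two assessors differ.
- Section 9.1 records infections, unscheduled medical episodes and admissions monthly for participants in every arm.
- Infections, antibiotic use and urgent care are endpoints, and 11.2 presents intervention effects with confidence intervals. An excess of chest infections, which are not on the 10.6 list, should therefore appear in a planned comparison.
- The DMC sees AE reports as well as SARs and can request more.
- The key sentence in 10.4 speaks of events related to the study population. Reading it as related to the product is an interpretation.
- By-arm safety tables may be in the SAP, which is not at hand, so their absence from the protocol is not itself a fault.
- No passage plans to declare the product safe from SAR counts.

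All of this stands, and it limits the point. It does not remove it. The rationale in 10.4, the exclusion in 10.6 and the DMC's named material are protocol text. No SAP can recover as SAEs events that were never recorded as SAEs. The DMC's power to ask for more depends on noticing a need, and the filtered data are what would show it.

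It is also fair that arm comparison is imperfect here. Care home staff know the allocation and may influence admission, and moderate excesses would be estimated too imprecisely to stand out.

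**Conclusion.** The point holds in limited form. Section 10.4 states a wrong principle for a randomised trial. Section 10.6 can keep serious events out of the AE/SAE data and contradicts 10.5.2. The DMC's named material does not use the plain-milk arm. An excess of common serious events could be missing from the AE/SAE data if the events are listed in 10.6, or from the SAR listing if they are rated below probable. It need not be missing from the infection, antibiotic, urgent care or admission data.

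The size of the gain rests on assumed risks and an assumed ICC. At 20% v 40%, 60 per arm and ICC 0.05, a by-arm table would show +20 points with a CI of about -2 to 42, while the chance that none of the 12 extra events is listed as a SAR is 7% to 54% for rating probabilities of 0.20 down to 0.05. At 10% v 20% the comparison has only 24% to 33% power. The table makes large excesses visible; it would not establish safety.

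**What to change.** - Replace the rationale in 10.4 with a statement that background events are separated from product effects by comparison with the plain-milk arm.
- Reconcile 10.5.2 with 10.6, so it is clear that an event meeting the SAE definition is recorded whatever its presumed cause.
- Keep causality grading for expedited reporting.
- In 15.5, and for the final report, name a table of all-cause deaths, SAEs and unplanned hospital admissions by coded arm, per resident-month. Show each supplemented arm against plain milk, plus the pooled contrasts (probiotic v none, fluoride v none). Present them as descriptive estimates with cluster-adjusted 95% CIs that allow for the small number of homes, in keeping with 11.2.

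The cost is protocol and DMC wording and one table, mostly from data already recorded. Serious events on the 10.6 list would add some recording. The downside is that background events and chance imbalances will appear and need explaining, with wide intervals.
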